Since the introduction of glucocorticoid and mineralocorticoid therapies in the 1950s, patients with classic CAH due to 21-hydroxylase deficiency generally survive infancy and childhood through to adolescence and adulthood. Glucocorticoid treatment is used not only to treat the adrenal insufficiency, but also to suppress ACTH and the downstream production of excess androgens. However, lifetime glucocorticoid (and mineralocorticoid) treatment alone is often not sufficient to control elevated androgen levels and sequelae of the disease, even when glucocorticoid is dosed at supraphysiological levels, as commonly occurs. The standard-of-care treatment itself, namely glucocorticoid treatment at supraphysiologic doses, presents its own significant health outcome risks and challenges for CAH patients, including iatrogenic Cushing's syndrome with obesity, hypertension, insulin resistance, diabetes, increased cardiovascular risk, decreased bone mineral density, and (in children) growth suppression (Elnecave et al., 2008; King et al., 2006; Migeon and Wisniewski, 2001). Importantly, there have been no new therapies developed for classic CAH since the 1950s and thus no other options besides glucocorticoid (and mineralocorticoid) treatment to manage the androgen excess.

Corticotropin-releasing factor is a hypothalamic hormone released directly into the hypophyseal portal vasculature and acts on specific CRF1 receptors on corticotropes in the anterior pituitary to stimulate the release of ACTH. Blockade of these receptors has been shown to decrease the release of ACTH in both animals and humans. Therefore, compounds that block CRF1 receptors have the potential to directly inhibit the excessive ACTH release that occurs in CAH and thereby

allow for normalization of androgen production while using lower, more physiologic doses of glucocorticoid. The novel CRF1 receptor antagonist, crinecerfont, may provide an important therapeutic approach to treat patients with CAH.

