## 9.8.2. Randomized, Double-Blind, Placebo-Controlled Treatment Period (Day 1 up to Week 28)

## **9.8.2.1.** Baseline (Day 1)

Baseline/Day 1 is defined as the first day of study drug dosing and should be the same as the day of randomization in the IRT.

Subjects should take their evening glucocorticoid dose prior to 2100 hours the night before the visit and should hold their morning dose of glucocorticoid and fludrocortisone (if applicable) on the day of the visit until after the predose blood sample collection, with dosing to occur between approximately 0800 and 0830 hours.

Subjects should be fasting, with no food from midnight the previous night until after the predose blood sample collection, after which they can have breakfast; subjects <6 years of age for whom the investigator deems that fasting until 0800 hours is not feasible can have a snack(s) if needed but should wait to have breakfast until after blood sample collection.

- Update inclusion/exclusion criteria as needed; subjects who continue to be eligible for the study will be randomized.
- Update medical history as needed.
- Perform a physical examination, including Tanner stage. Tanner stage will not be required to be assessed at Day 1 if the investigator determines that the Tanner stage is unlikely to have changed since screening; in this case, the screening Tanner stage will be considered the baseline.
- Perform vital signs, height, and weight.
- Collect blood samples for chemistry, TSH, free T4, hematology, and coagulation labs; fasting lipids and HOMA-IR; cortisol, LH, FSH, testosterone, PRA.

- Collect blood samples for 17-OHP, A4, and ACTH.
  - For subjects who are ≥6 years of age with a body weight ≥20 kg: approximately 15 minutes before and just prior to dosing with the morning glucocorticoid and at 2, 3, 4, and 6 hours after dosing. Any midday glucocorticoid dose that the subject is receiving should be taken after the 6-hour postdose blood sample collection. For subjects with body weight ≥20 to <30 kg, only a single sample for ACTH will be collected, which will be the sample just prior to the morning glucocorticoid dose.

  - For subjects who are <6 years of age or with a body weight <20 kg: blood sample collected prior to dosing with the morning glucocorticoid.

- Collect urine sample for urinalysis and (only for subjects of childbearing potential) urine pregnancy test.

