## 9.8.2.7. Week 28 (±7 days; all Week 28 assessments should be completed before a subject begins open-label treatment)

Subjects should take their evening glucocorticoid dose prior to 2100 hours the night before the visit and should hold their morning dose of glucocorticoid, fludrocortisone (if applicable), and study drug on the day of the visit until after the predose blood sample collection, with dosing to occur between approximately 0800 and 0830 hours with breakfast.

Subjects should be fasting, with no food from midnight the previous night until after the predose blood sample collection, after which they can have breakfast; subjects <6 years of age for whom the investigator deems that fasting until 0800 hours is not feasible can have a snack(s) if needed but should wait to have breakfast until after blood sample collection.

- Perform a physical examination.
- Perform vital signs, height, and weight.
- Assess Tanner stage (only if Tanner stage <5 on Day 1).
- Collect blood samples for chemistry, TSH, free T4, hematology, and coagulation labs; PK (prior to morning study drug); fasting lipids and HOMA-IR; 17-OHP, A4, cortisol, ACTH, LH, FSH, testosterone, and PRA prior to dosing.
- For subjects ≥6 years of age with body weight ≥20 kg, also collect blood samples for 17-OHP, A4, and ACTH approximately 3 hours after glucocorticoid and study drug administration.
- Collect urine sample for urinalysis and (only for female subjects of childbearing potential) urine pregnancy test.
- Collect salivary samples for hormone assessment at approximately 0600 hours, at approximately 0800 hours prior to morning glucocorticoid dosing and 3 and 6 hours after dosing (any midday glucocorticoid dose that the subject is receiving should be taken after the salivary sample collection 6 hours after dosing), and within 30 minutes prior to the evening dose of glucocorticoid; if subject is not on an evening glucocorticoid dose, then prior to bedtime.

- Perform x-ray to assess bone age (only in females with the most recent bone age <14 years and in males with the most recent bone age <16 years; see Section 9.3.4).
- Perform testicular ultrasound (males only; only if evidence of TART on Day 1 ultrasound).

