#### 13.6.1.3. Key Secondary Endpoints

The first key secondary endpoint is the change from baseline in serum 17-OHP at Week 4. Both baseline and Week 4 serum 17-OHP values for subjects ≥6 years of age with a body weight ≥20 kg will be calculated as the average of all serum 17-OHP values obtained from serial sampling on Day 1 and Week 4, respectively (subjects <6 years of age or <20 kg will have only a single serum 17-OHP value for both baseline and Week 4). The primary analysis of this endpoint will be performed using an ANCOVA model. The model will include treatment group, baseline serum 17-OHP, and stratification factors used in the randomization. Subjects who are missing serum 17-OHP levels at all time points at the Week 4 visit will have their data imputed through a multiple imputation procedure. Missing data will be imputed for subjects in the crinecerfont treatment group using retrieved data (ie, observed data from subjects who discontinued study drug) in the crinecerfont treatment group, provided there is sufficient retrieved data. Otherwise, missing data will be imputed using observed data from any subject in the placebo treatment group. For subjects in the placebo treatment group, missing data will be imputed using observed data from any subject in the placebo treatment group.

The second key secondary endpoint is the percent change from baseline in glucocorticoid daily dose (in hydrocortisone dose equivalents adjusted for BSA [mg/m²/day]) at Week 28, while Week 28 serum A4 is ≤120% of the baseline value or ≤ ULN, according to sex and either age (for Tanner stage 1) or pubertal stage (for Tanner stages 2 to 5). For all subjects, baseline serum A4 will be defined as the average of all pre-morning glucocorticoid serum A4 values on Day 1 (for subjects who are <6 years of age or with a body weight <20 kg, only the single pre-morning glucocorticoid serum A4 value will be used). If values on Day 1 are missing, the last pre-morning glucocorticoid serum A4 value prior to Day 1 will serve as the baseline. The pre-morning glucocorticoid dose A4 value at Week 28 will be used for the comparison to the baseline A4 in assessing control (as defined above). Of note, 1 mg of methylprednisolone, prednisolone, or prednisone will be converted to 4 mg of hydrocortisone for the purpose of determining the hydrocortisone dose equivalents. The primary analysis of this endpoint will be performed using an ANCOVA model. The model will include treatment group, baseline

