glucocorticoid daily dose, and stratification factors used in the randomization. This analysis will be performed using the FAS.

Subjects who have a decrease in glucocorticoid daily dose at Week 28 and who are not able to maintain their serum A4 at Week 28 at ≤120% of their baseline value or ≤ ULN for sex and either age (for Tanner stage 1) or pubertal stage (for Tanner stages 2 to 5) will be considered to have a zero percent change from baseline in the glucocorticoid daily dose at Week 28. Subjects who are missing glucocorticoid dose at Week 28, serum A4 levels at all time points at the Week 28 visit, or time point-matched serum A4 values at baseline and Week 28 will have their data imputed through a multiple imputation procedure. Missing data will be imputed for subjects in the crinecerfont treatment group using retrieved data (ie, observed data from subjects who discontinued study drug) in the crinecerfont treatment group, provided there is sufficient retrieved data. Otherwise, missing data will be imputed using observed data from any subject in the placebo treatment group, missing data will be imputed using observed data from any subject in the placebo treatment group.

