## 6.3.5. Baseline Definition of Serum Androstenedione "Control" for Second Key Secondary Endpoint

The second key secondary endpoint is the percent change from baseline in glucocorticoid daily dose (in hydrocortisone dose equivalents adjusted for BSA [mg/m^2/day]) at Week 28, while androstenedione is in "control". Androstenedione is considered in "control" if the Week 28 serum androstenedione is  $\leq 120\%$  of the baseline value or  $\leq ULN$ , according to sex and either age (for Tanner stage 1) or pubertal stage (for Tanner stages 2 to 5). For all subjects, baseline serum androstenedione used to define "control" will be defined as the average of all pre-morning glucocorticoid serum androstenedione values on Day 1. Subjects who are <6 years of age or <20 kg will have only a single pre-morning glucocorticoid serum androstenedione value for baseline and Week 28. If values on Day 1 are missing, the last pre-morning glucocorticoid serum androstenedione value prior to Day 1 will serve as the baseline. The pre-morning glucocorticoid

dose androstenedione value at Week 28 will be used for the comparison to the baseline androstenedione in assessing control (as defined above). If the pre-morning glucocorticoid dose androstenedione value at Week 28 is not available, the post-morning glucocorticoid dose value will be used. The missing data handling approach is described in Section 9.4.2.

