### 9.3.2. Primary Efficacy Analysis

The primary efficacy endpoint is the change from baseline in serum androstenedione at Week 4. The definitions of the baseline and Week 4 serum androstenedione values that will be used in this analysis are described in Section 6.3.3. The primary analysis of the primary endpoint will be performed using an ANCOVA model, as described in Section 9.2.1. The model will include treatment group, baseline serum androstenedione (as defined in Section 6.3.3), and stratification factors used in the randomization.

Subjects who are missing serum androstenedione at all timepoints at the Week 4 visit will have their data imputed through the multiple imputation procedure described in Section 17.1.

Statistical significance for the treatment comparison will be determined using the multiple comparison procedure described in Section 9.1. Descriptive statistics and LS means will be presented by treatment group along with the LS mean treatment difference, 95% confidence intervals, and p-value.

Descriptive statistics will be presented for serum androstenedione by treatment group and visit from baseline through Week 28. For visits where androstenedione is collected more than once (eg, Day 1; Week 4), the average of the visit values will be analyzed. For visits where more than one pre-morning GC dose sample is collected, the average of the pre-morning GC dose will be analyzed; otherwise, the pre-morning GC dose is the single value collected. Observed and change from timepoint-matched baseline values will be summarized for visit average values and pre-morning GC dose values. The androstenedione observed values from the screening visit will also be summarized.

Mean (±SEM) values of serum androstenedione at each visit will be summarized in line graphs by treatment group. Pre-morning GC dose values and visit average values will be presented on separate plots. Similar graphs will be presented for the changes from baseline.

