### 14. DEVIATIONS FROM PROTOCOL PLANNED ANALYSIS

This section will document any deviations from the protocol planned analysis along with any assessments that were performed on study (and reviewed by the study site) but will not be summarized.

The following assessments were performed on study but will not be summarized:

- Physical examination results (excluding height, weight, and Tanner staging)
- CYP21A2 genotyping
- Pregnancy test
- Urine drug screen
- Urinalysis
- Glucocorticoid daily dose from eDiary

The following list includes all deviations from the protocol planned analysis:

- The Safety Analysis Set definition in the protocol specified that the subject must have postbaseline safety data during the double-blind placebo-controlled period. This part of the definition was removed from the SAP due to the potential issue of having a subject dosed with study drug and then becoming lost to follow-up.
- The Safety Analysis Set was split up into the DB Period Safety Analysis Set and the OL Period Safety Analysis Set.

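### SAP 6.3.5 allows a Week 28 androstenedione drawn about 3 hours after the morning glucocorticoid to be judged against a pre-dose baseline, contrary to the protocol and undeclared

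*SAP*

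**What the plan says.** **Protocol 13.6.1.3.** The A4 baseline for control is the average of the Day 1 values taken before the morning glucocorticoid. For Week 28: "The pre-morning glucocorticoid dose A4 value at Week 28 will be used for the comparison to the baseline A4 in assessing control". The protocol then sends three groups to imputation: subjects lacking the Week 28 dose, those lacking every Week 28 A4 value, "or time point-matched serum A4 values at baseline and Week 28 will have their data imputed through a multiple imputation procedure".

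**SAP 6.3.5.** This keeps the pre-dose Day 1 baseline for all subjects and the pre-dose Week 28 value, but adds a fallback: "If the pre-morning glucocorticoid dose androstenedione value at Week 28 is not available, the post-morning glucocorticoid dose value will be used".

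**Sampling.** The only scheduled post-dose A4 at Week 28 is in subjects aged at least 6 years and weighing at least 20 kg. For them protocol 9.8.2.7 says to "also collect blood samples for 17-OHP, A4, and ACTH approximately 3 hours after glucocorticoid and study drug administration". On Day 1 the same age and weight group is sampled "approximately 15 minutes before and just prior to dosing with the morning glucocorticoid and at 2, 3, 4, and 6 hours after dosing" (protocol 9.8.2.1), so a 3-hour Day 1 value is also scheduled.

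**SAP 9.4.2 and 17.2.** A subject whose dose fell but whose A4 is not controlled is given a change of 0%. Section 9.4.2 triggers imputation when the dose and A4 at every Week 28 time point are missing. Section 17.2 triggers it when either or both are missing, and its models use pre-dose A4 only.

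**SAP Section 14.** "The following list includes all deviations from the protocol planned analysis". The list has two entries, both about the Safety Analysis Set.

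**The concern.** Control of A4 decides whether a dose reduction counts in an endpoint that is third in the alpha-controlled sequence. Under the fallback, that decision compares a value taken about 3 hours after glucocorticoid and study drug with one taken before glucocorticoid. Protocol 5.1 gives the reason to expect a difference: "Glucocorticoid treatment is used not only to treat the adrenal insufficiency, but also to suppress ACTH and the downstream production of excess androgens". The likely direction is a lower post-dose value, and so a finding of control that the pre-dose value might not have supported. The upper limit of normal (ULN) limb is loosened in the same way as the 120% limb.

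A reduction that 9.4.2 would set to 0% could then be credited, and the same subject could count as a responder, because SAP 9.5.1 follows the conventions of 9.4.2. Most of the supporting analyses inherit the decision. The 150% and 180% analyses in 9.4.2.2 change only the threshold. The latest-dose and highest-dose analyses, and the tipping point analysis in 17.5, start from the same Week 28 control status.

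**Working it through.** **1. The plan's own figure.** The only power figure concerns the Week 4 primary endpoint. The effect size is 286.2/345.02 = 0.83. With 54 and 27 subjects and two-sided 0.05, a two-sample t-test gives 93.6% power at 0.83 and 83.5% at 0.70, so the stated figures of above 90% and above 80% reproduce. This point does not affect them.

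**2. The texts side by side.**

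| Question | Protocol 13.6.1.3 | SAP |
|---|---|---|
| Baseline A4 for control | Pre-dose Day 1 | Pre-dose Day 1 (6.3.5) |
| Week 28 A4 for control | Pre-dose | Pre-dose, otherwise post-dose (6.3.5) |
| No time-matched pair | Impute | Condition absent (9.4.2) |
| Declared as a change | – | Not in Section 14 or the version table |

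For a subject with only a 3-hour Week 28 A4, 6.3.5 and 9.4.2 read as if A4 is present. Section 17.2 takes the A4 it needs from 6.3.5, yet models only the pre-dose value, which is missing. It does not say which applies.

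**3. How far the threshold could move.** The documents give no 3-hour fall, so a fall x is assumed. A post-dose value exactly at the limit corresponds to a pre-dose value of limit/(1 − x).

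| Assumed fall x | 120% limb: 120%/(1 − x) | ULN limb: 100%/(1 − x) |
|---|---|---|
| 20% | 150% of baseline | 125% of ULN |
| 30% | 171% of baseline | 143% of ULN |
| 50% | 240% of baseline | 200% of ULN |

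**4. Effect of one wrongly credited subject on the arm mean.** Assume a dose of 12 mg/m²/day (the entry limit in inclusion criterion 4; entry requires more than this) falling to the protocol's target range of 8 to 10. The reduction R is (12 − 10)/12 = 16.7% to (12 − 8)/12 = 33.3%. A higher starting dose gives a larger R.

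- Against a change set to 0%, the shift is R/n: 16.7/54 = 0.31 to 33.3/54 = 0.62 points for crinecerfont, and 16.7/27 = 0.62 to 33.3/27 = 1.23 points for placebo.
- Against imputation, suppose a share p of the 100 imputed A4 values shows control. The observed dose is then kept in a share p of datasets and set to 0% in the rest, so the shift is (1 − p)R/n.

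| p | Crinecerfont, n = 54 | Placebo, n = 27 |
|---|---|---|
| 0.25 | 0.23–0.46 points | 0.46–0.93 points |
| 0.50 | 0.15–0.31 points | 0.31–0.62 points |
| 0.75 | 0.08–0.15 points | 0.15–0.31 points |

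**5. Responder rate.** Against non-response, one subject moves the rate by 100/54 = 1.9 points or 100/27 = 3.7 points. Against imputation, multiply by (1 − p): 0.5 to 1.4 points or 0.9 to 2.8 points for p from 0.75 to 0.25.

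These are shifts in raw arm means and rates, not in the covariate-adjusted treatment difference.

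**The case against.** The strongest objection is that the rule may never be used. It needs a subject in the older, heavier group with a usable 3-hour A4 but no usable pre-dose A4, although the pre-dose sample is drawn first at the same visit. Both arms follow the same rule. This stands as a limit on size; the case rests on the rule as written, not on a demonstrated effect.

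The direction is inferred from background on glucocorticoid therapy, and the falls are assumed. That also stands. So does the remark that the protocol would impute such a subject and not set the change to 0%, which makes the smaller figures in step 4 the fairer comparison.

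The protocol's reference to A4 missing at every time point can be read as tolerating a post-dose value. At most this admits 3-hour against 3-hour; the time-matching clause still excludes 3-hour against pre-dose.

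The SAP's own descriptive standard, "Observed and change from timepoint-matched baseline values will be summarized for visit average values and pre-morning GC dose values", is only partial support. A Week 28 visit average has fewer samples than the Day 1 average, so matching there is not strictly by clock time. It does keep pre-dose values and visit averages apart, which the fallback does not.

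One analysis in 9.4.2.2 uses doses regardless of A4, so for observed doses the fallback has no part in it. It answers a different question from reduction with control maintained.

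**Conclusion.** The concern holds. The SAP permits an unmatched control decision in an alpha-controlled endpoint, this departs from protocol 13.6.1.3, and Section 14 does not declare it. These three statements follow from the text and do not depend on the assumed figures. The lean towards control is an inference. The number affected (possibly zero), the size of the 3-hour fall and the net effect on the treatment difference cannot be found in the documents. Per subject, the effect is below one percentage point on an arm mean under the imputation comparison and the inputs above. It should be fixed because it is a stated rule that can be corrected before unblinding, and because 9.4.2 and 17.2 leave two programmers free to handle the same subject differently.

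**What to change.** **SAP 6.3.5.** Remove the unmatched comparison in one of two ways and run the other as a sensitivity analysis.

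- Option A: treat a missing pre-dose Week 28 A4 as missing and impute it under 17.2. This covers both limbs of the control definition.
- Option B: compare the 3-hour Week 28 value only with the 3-hour Day 1 value, and impute if the latter is missing, for example in a subject below 20 kg on Day 1. Also state which Week 28 value the ULN limb uses, because matching repairs only the 120% limb. Inclusion criterion 5 applies the A4 reference range to a pre-dose value.

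**SAP 9.4.2.** Trigger imputation when the Week 28 dose, the A4 value that 6.3.5 uses for control, or both are missing.

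**SAP 17.2.** State how a subject with only a 3-hour Week 28 A4 is handled.

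**SAP Section 14.** List any departure that is kept. Before unblinding, report the blinded count of subjects with a 3-hour but no pre-dose Week 28 A4.

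**Secondary alignment.** Sections 9.3.2 and 9.4.1 still trigger Week 4 imputation only when every time point is missing, although those endpoints now use pre-dose values. Refer to the pre-dose values instead. The Week 4 change from serial to pre-dose averages, for A4 and 17-OHP, is in the version table and should also be in Section 14.

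**Cost.** SAP wording only, with no new data. Option A adds a little imputation, which can credit an uncontrolled subject in some of the 100 datasets and withhold credit from a controlled one in others. Option B adds a small matched comparison.
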